7.4. Complaint Handling

Any feedback from participants of each site will be taken seriously and concerns will be brought up to the PI to follow up.

8. SAMPLE SIZE AND STATISTICAL METHODS

8.1. Determination of Sample Size.

Since this is a pilot trial, we aim to recruit 60 participants to account for a ~20% dropout rate, ensuring we meet our target of at least 50 participants.

8.2. Statistical analyses.

Our confirmatory statistical analyses will include:

- Bayesian mixed-effects models to investigate the longitudinal changes in self-reported stress measured via STAI-6. The model will have STAI-6 as the

dependent variable, with 'Group' (mindfulness intervention or control), 'Day' (1 to 3), and their interaction term as independent variables. Participant ID will be used as a random intercept to control for individual differences. A BF10 greater than 1 will indicate slightly positive evidence supporting the effectiveness of the mindfulness condition over the control condition in stress reduction.

We will also conduct the following exploratory statistical analyses:

- A Bayesian mixed-effects model to assess longitudinal changes in HRV, using HRV as the dependent variable and 'Group', 'Day' (1 to 3), and their interaction as independent variables. Participant ID will again serve as a random intercept. A BF10 greater than 1 will suggest positive evidence for the mindfulness intervention's effectiveness compared to the control.
- An additional Bayesian mixed-effects model will analyze longitudinal changes in HRV, with the dependent variable being HRV (calculated by the difference in pre- and post-meditation HRV scores) and independent variables including 'Group', 'Day' (1 to 3), and their interaction. Participant ID will account for individual variability in baseline HRV levels.
- Correlational analyses to explore the relationship between changes in mindfulness scores and stress levels, as well as between HRV changes and stress levels.
- Descriptive statistics to summarize baseline participant characteristics, such as neuroticism, RS-14 scores, FFMQ scores related to mindfulness training, and demographic details.
- Analysis of responses regarding the intervention's credibility and participant awareness of the research hypothesis to assess equal credibility of the intervention for the mindfulness condition and the sham.

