4. STUDY POPULATION

4.1. Number and nature of participants to be enrolled.

Being this a pilot study, the target recruitment is set at 60 participants, aged 21 or older.

4.2. Criteria for Recruitment and Recruitment Process.

Participants will be recruited from the general Singaporean community. To streamline the recruitment process, we will utilize the broad reach of social media platforms, including Facebook, Instagram, and X (formerly Twitter), where we will post a detailed description of the study.

Interested individuals will be directed to complete an online form (e.g. FormSG, Microsoft Forms etc), where they will answer questions related to the inclusion and exclusion criteria and provide a phone number for potential follow-up by the study coordinator. Those who meet the inclusion criteria will be contacted via phone (e.g. WhatsApp) by the study coordinator, who will guide them through the subsequent steps outlined in the procedure section.

The study coordinator will review the form responses daily and will close the link once 60 participants have been confirmed as meeting the inclusion criteria.

The trial involves a brief, fully anonymized online survey conducted over three consecutive days, with Day 1 and Day 3, requiring a commitment of approximately 35 minutes and Day 2 a commitment of 25 minutes. Given the study's minimal risk, non-invasive nature, and the absence of medication administration, we will seek an exemption from the requirement for traditional written consent.

To further enhance recruitment, we will collaborate with ASTAR's administrative team to notify potential participants in their database who have consented to receive research-related communications. Information about the study will also be shared through ASTAR's internal channels, in full compliance with digital platform regulations.

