5.4 Study procedures

Participants expressing interest will first complete an initial online screening form (e.g., via FormSG or Microsoft Forms), containing non-sensitive questions to assess eligibility based on study criteria such as English proficiency, age, meditation experience, vision and hearing capabilities, willingness to commit to the study procedures, and any relation to A*STAR research team members. Participants will also provide their phone number, which will be used to notify them of their eligibility status. The phone number will be retained until the end of data collection to prevent repeat participation, facilitate the delivery of study materials, and ensure compensation via e-vouchers. The study coordinator will check whether a mobile number has been previously used and stop participants if a duplicate number is detected.

Once the study coordinator reviews the responses daily, eligible participants (i.e., those meeting inclusion and exclusion criteria and those who provided a phone number not previously entered in the survey), will receive a standardized text

message (e.g., via WhatsApp) confirming their preliminary eligibility. For ineligible participants, their collected data will be discarded. If eligible, participants will be informed that the study will begin within three weeks. Upon the recruitment of the 20th participant or at the end of the third week, the coordinator will notify the cohort, instructing them to start the study within two days. The study will consist of three cohorts of 20 participants each. If fewer than 60 participants are recruited after the third cohort, an additional cohort will be organized to reach the target number.

At this point, participants will receive a message containing the following: a link to access the Qualtrics survey, an access code (which serves as an anonymous identifier), and a link to instructions for downloading the 'Camera Heart Rate Variability' app, used for heart rate variability (HRV) measurement. The instructions will detail how to take measurements and submit the generated HRV.csv data files to the study team. Participants will also receive a code to download the app for free. They will be advised to complete the survey each day at the same time, between 9 am and 9 pm.

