The Qualtrics link contains the written informed consent form and the actual experiment. Participants will be able to review all relevant information about the study and either accept or decline to participate. If they do not provide consent, they will be opted out of the study. If consent is provided, participants will proceed to the second screening, which involves answering additional questions about their use of concomitant medication. If they meet the criteria for this stage, they will proceed to answer questions about any neurological or psychiatric conditions. If any of the screening criteria are not satisfied at any point, the study will automatically terminate. Once consent and second screening are complete, participants will then be instructed to move to a quiet environment where they will not be disturbed for the next 35 minutes. They will be asked to download the 'Camera Heart Rate Variability' app and take an initial HRV measurement for testing purposes. Participants will then submit the generated CSV file to the study coordinator via WhatsApp and self-report their rMSSD values in the Qualtrics survey. Participants are instructed to label their CSV files using their anonymous identifier provided by the study coordinator via WhatsApp at the start. Afterward, they will complete a series of questionnaires, including the 20-item IPIP scale, the RS-14, the FFMQ, and various demographic questions such as age, gender, ethnicity, smartphone type used during the experiment, and its operating system (iOS or Android) and version. Pre-intervention assessments of STAI-6, EMA will also be conducted. They will then use the 'Camera Heart Rate Variability' app to measure HRV, submit the generated CSV file to the study coordinator, and self-report their rMSSD values in the Qualtrics survey, as outlined in the instructions.

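### Section 8.1: 60 recruits with about 20% dropout leave 48, not the stated minimum of 50 (a minor arithmetic correction)

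*Combined protocol and SAP*

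**What the plan says.** Section 8.1 is the whole of the sample-size justification. It reads: "we aim to recruit 60 participants to account for a ~20% dropout rate, ensuring we meet our target of at least 50 participants". It gives no source for the dropout rate and does not show how 60 was obtained. The figure of 50 appears nowhere else as a target.

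The other sections that bear on numbers concern recruitment, not retention. Section 4.1 repeats the target of 60. Section 4.2 says the coordinator "will close the link once 60 participants have been confirmed as meeting the inclusion criteria". Section 5.4 plans three cohorts of 20 and adds: "If fewer than 60 participants are recruited after the third cohort, an additional cohort will be organized to reach the target number". Section 4.5 lets participants withdraw at any time and says nothing about replacing them.

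**The concern.** Section 8.1 offers 60 as enough to absorb the assumed dropout and still leave 50. A reader who applies the stated rate to the stated number gets 48, which is under the stated floor. Either the recruitment number, the dropout rate or the target must be wrong as written.

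The stake is modest: a public plan whose only sample-size statement contradicts itself. Section 1 presents this pilot as groundwork for a multi-site trial, so its retention allowance may well be reused there, and it should be right.

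**Working it through.** **Inputs, all from section 8.1:** recruits N = 60; dropout d = 0.20 (given as approximate); target after dropout T = 50.

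**Step 1. Reproduce the plan's 60.** Adding 20% to the target gives T × (1 + d) = 50 × 1.20 = 60, which matches exactly. The document shows no derivation, so this is only a likely explanation.

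**Step 2. Apply the dropout to those recruited.** N × (1 − d) = 60 × 0.80 = 48, which is 2 below the target. In losses, 60 × 0.20 = 12, while the target allows 60 − 50 = 10.

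**Step 3. Find the dropout rate at which 60 gives 50.** 10/60 = 16.7%.

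**Step 4. Find the number needed at 20%.** T/(1 − d) = 50/0.80 = 62.5, rounded up to 63. Check: 62 × 0.80 = 49.6 and 63 × 0.80 = 50.4.

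**Step 5. See how the result moves with the rate.**

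| Dropout | Expected to remain from 60 |
|---|---|
| 15% | 51.0 |
| 16.7% | 50.0 |
| 18% | 49.2 |
| 20% | 48.0 |
| 25% | 45.0 |

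**Step 6. Look for a rule that closes the gap.** The form-closing rule in section 4.2 stops at 60 eligible people. The extra cohort in section 5.4 is triggered by fewer than 60 recruited. Section 8.1 itself treats the number recruited (60) and the number left after dropout (50) as different quantities, so a top-up to 60 recruited does not secure 50 remaining. No section replaces dropouts or ties recruitment to the number retained.

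**The case against.** **The rate is only approximate.** Ten losses of 60 is 16.7%, which rounds to 20% at one significant figure, so a loose reading makes 60 and 50 agree on average. This stands in part: it shows how small the slip is. But at the rate actually printed the expected number is 48, and even on the loose reading 50 is an expected value, not an assured minimum.

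**Nothing depends on 50.** This stands. The plan makes no power, precision or Bayes-factor claim at that number. Section 8.1 also does not say that the 50 must complete all three days. The confirmatory analysis in section 8.2 is a mixed-effects model with a random intercept, which can use the earlier days of someone who misses a later one, although the plan states no rule for missing data.

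**A reader might infer a larger failure from the probabilities.** If dropouts are independent, the chance of keeping 50 or more of 60 is about 32% at 20% dropout and 58% at 16.7%. These figures should not be counted as a further defect. Inflating for dropout ordinarily aims at an expected number, and even a correctly inflated 63 gives only about a 62% chance of 50 or more at 20% dropout. The plan sets no probability that it must meet.

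**A reader might also infer a further shortfall before randomisation.** Section 5.4 describes the first message to eligible people as "confirming their preliminary eligibility". It then says "Upon the recruitment of the 20th participant or at the end of the third week, the coordinator will notify the cohort", and the survey link comes at that point. Of that link it says: "The Qualtrics link contains the written informed consent form and the actual experiment". On this reading the 60 are counted before consent and second screening, and losses there would use up the same margin of 10. The documents do not establish such a shortfall. They do not define when a person counts as recruited, do not say whether the 20% already covers these losses, and give no rate for them. Redefining the 60 as randomised participants would also clash with section 5.4, where the 20th recruitment must come before the link that carries consent, and where three cohorts of 20 make up the 60.

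**Conclusion.** The point holds as an arithmetic error in one sentence. At the plan's own rate, 60 recruits leave an expected 48, two short of the stated 50. The figures agree only if dropout is about 16.7%, or if 63 are recruited at 20%.

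This takes the 20% at face value and as a share of the 60 recruited, which is how the sentence reads. The correction is worth making because the sentence is wrong as written and cheap to repair. It is minor: the gap is two participants in a pilot without a power claim, no stated analysis changes, and the validity of the trial is not in question.

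**What to change.** In section 8.1, keep 60, delete 'ensuring', and use one of two consistent statements:

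- about 48 participants are expected to remain at 20% dropout, with the target of 50 lowered to match; or
- an expected 50 will remain if dropout is about 17% (10 of 60), with the assumed dropout rate changed to match.

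Whichever is chosen, the target and the dropout rate must be changed together, so that neither is dropped without saying so.

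The cost is one sentence. The sponsor must accept either a slightly lower stated target or a slightly more favourable dropout assumption. Keeping 60 leaves sections 4.1 and 4.2 and the three cohorts of 20 in section 5.4 untouched. Raising the number to 63 would also be arithmetically consistent, but those sections would then have to change for a gain of 50.4 − 48 = 2.4 expected participants.

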2. AIMS AND HYPOTHESES

This pilot study seeks to assess the impact of a three-day mindfulness intervention on the stress response of Singaporean adults aged 21 or more. Specifically, we will anticipate a modest yet discernible reduction in stress levels compared to a control condition, represented by a sham meditation group.

In addition to evaluating the effectiveness of the decentralized mindfulness intervention and its comparison with the sham meditation control group, this study will also incorporate an assessment of the credibility and usability of the survey-based methodology employed.

Participants' feedback regarding the clarity of survey instructions, ease of navigation, and overall user experience will be solicited through post-intervention questionnaires. Insights gleaned from participants' perspectives will inform refinements to the methodology, ultimately optimizing its utility for a fully decentralized study on mindfulness on a larger scale.

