5.3.2 Pre and post measurements

The Five Facet Mindfulness Questionnaire – Short Form (FFMQ-SF; Bohlmeijer et al. 2011). The scale is recommended for comparing pre and post interventions that employ mindfulness training. The scale measures 5 different components; *Observing*; the ability to notice and pay attention to the thoughts, feelings, and surroundings. *Describing*; the attitude to express the experiences in words, to describe thoughts and emotions. *Acting with Awareness*; How well they can act with intention and full awareness in their daily activities, rather than on autopilot. *Non-judging of Inner Experience*; tendency to avoid judging their thoughts and emotions as good or bad. *Non-reactivity to Inner Experience*; tendency to experience thoughts and emotions without reacting impulsively. However, recent hierarchical confirmatory factor analysis indicates a preference for a four-factor FFMQ (excluding the 'observe' subscale) in non-meditative samples, as opposed to the traditional five-factor score (Gu et al., 2016). Consequently, the analysis will focus on four facets: Describing,

acting with awareness, non-judging, and non-reactivity. Examples of items are "I can describe my feelings well" or "I can easily talk about my thoughts and opinions" (answered on a five-point scale ranging from 1 = never or very rarely to 5 = Very often or always true). We will take this assessment at baseline and at the end of the experiment.

Repeated measurements (day 1, day 2, day 3)

State Trait Anxiety Inventory (STAI-6; Marteau TM, Bekker) The STAI-6 is a validated short-form version of the 40-item State-Trait Anxiety Inventory (STAI), consisting of 6 items that measure current anxiety symptoms using a 4-point Likert scale. Example items include statements such as "I feel calm" and "I am tense." The STAI-6 will be administered twice daily: once before and once after listening to each audio track.

Ecological Momentary Assessment – (EMA) Participants will indicate their current state on a 7-point Likert scale, with the options "Very Bad," "Bad," "Fairly Bad," "Same as Before," "Fairly Good," "Good," and "Very Good," encoded as [1, 2, 3, 4, 5, 6, 7], respectively. The following questions will be posed to assess various psychological and physical states:

- "Right now, I feel mentally sharp" – to assess perceived cognitive ability.
- "Right now, I feel fatigued" – to assess fatigue and exhaustion.
- "Right now, I feel stressed" – to assess stress levels.

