- "Right now, I feel nervous" – to assess nervousness and tension.
- "Right now, I feel depressed" – to assess depressive symptoms.
- "Right now, I am in a good mood" – to assess positive affect and joy.
- "I slept well last night" – to assess subjective sleep quality.

Ecological Momentary Assessment (EMA) will be conducted twice daily, immediately following each administration of the STAI-6 questionnaires.

Heart Rate Variability. To assess parasympathetic activation, participants' heart rate variability (HRV) will be analyzed. HRV is widely recognized as a sensitive marker of stress, regulated by the autonomic nervous system in response to stressors (Goldberger et al., 2001). Participants will monitor their HRV using the 'Camera Heart Rate Variability' smartphone app, which employs Photoplethysmogram (PPG) technology. Notably, smartphone apps utilizing PPG for heart rate measurement have shown consistency with validated methods such as electrocardiography (ECG) in adult populations during resting states (Gudeo-Fernández et al., 2020).

Participants will assess their HRV values seven times over the course of the trial (from Day 1 to Day 3). Participants will be instructed to place their index finger over the smartphone's camera and flash, ensuring both are fully covered. They will hold their finger in place for one minute to allow the device to record their heart rate variability (HRV). Upon completion, the HRV measurement will be saved in the app's local folder. If the finger placement is inadequate, resulting in poor assessment quality, the app will indicate that the CSV file has not been created. In such cases, participants will be asked to repeat the assessment up to two more times. If they are still unable to obtain a valid measurement after the third attempt, they will be instructed to proceed to the next section of the survey.

Participants will then send the corresponding CSV file via email to the study coordinator using a feature included in the app, following the instructions provided at the beginning of the experiment. To ensure that HRV data is not lost, participants will also self-report the corresponding values in the Qualtrics survey.

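### The confirmatory outcome, STAI-6, is defined as anxiety but analysed and interpreted as stress with no stated rationale, and the direct stress item has no planned group comparison

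*Combined protocol and SAP*

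**What the plan says.** Section 2 (Aims and hypotheses) anticipates "a modest yet discernible reduction in stress levels compared to a control condition", the control being sham meditation.

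Section 5.3.2 introduces STAI-6 as a short form of an anxiety inventory, "consisting of 6 items that measure current anxiety symptoms using a 4-point Likert scale". It is given before and after each audio track on Days 1 to 3. The same section lists seven EMA statements. One is "Right now, I feel stressed", whose stated purpose is to assess stress levels; a different one is there "to assess nervousness and tension". The EMA "will be conducted twice daily, immediately following each administration of the STAI-6 questionnaires".

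Section 8.2 has one confirmatory analysis, a Bayesian mixed-effects model of "longitudinal changes in self-reported stress measured via STAI-6" with Group, Day and their interaction as predictors and a random intercept per participant. BF10 above 1 is to be read as slightly positive evidence "supporting the effectiveness of the mindfulness condition over the control condition in stress reduction". Two exploratory mixed models use HRV as the outcome. Exploratory correlations relate changes in mindfulness scores, and changes in HRV, to stress levels, without saying which instrument supplies those levels. EMA is not named anywhere in section 8.2.

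**The concern.** The same score carries one meaning where the instruments are described and another where the result is interpreted. A finding on six anxiety items would be reported as a finding on stress. Stress is the subject of the aim, and section 1 says the planned multi-site study is to test whether the stress-reducing effect of mindfulness is genuine.

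The one self-report item that asks about stress in so many words has no assigned role in the comparison of mindfulness with sham. With no role fixed in advance, it could be reported or left out once the data are known. Section 9 says the study will be publicly registered, so the label given to the outcome will be carried forward.

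**Working it through.** No figure in the plan bears on this point, so the check sets the definition of each measure beside its use.

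| Measure | Defined as | Use in section 8.2 |
|---|---|---|
| STAI-6 | Current anxiety symptoms (5.3.2) | Outcome of the one confirmatory model; labelled and concluded upon as stress |
| EMA stress item | Stress levels (5.3.2) | Not named; outcome in no model |
| EMA nervousness item | Nervousness and tension (5.3.2) | Not named |
| HRV | Physiological measure of the stress response (1) | Outcome of two exploratory models |

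1. **Is a bridge from anxiety to stress given?** No. Neither section 5.3.2 nor section 8.2 gives a rationale, a validation result or a reference for STAI-6 as a stress measure. The cited source for STAI-6 is, by its title in the reference list, a short form of an anxiety scale.

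2. **Does the protocol treat the two as one construct?** Its own item list does not. Stress and nervousness or tension get separate EMA items, and one of the two STAI-6 examples in section 5.3.2 is about being tense, which is nearer to the second item.

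3. **Is the stress item available where it is needed?** Yes. EMA follows every STAI-6 administration: 2 per day × 3 days = 6 readings per participant. At the target of 50 retained participants (section 8.1) that is 50 × 6 = 300 paired readings of STAI-6 and the stress item.

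4. **Is there a group comparison on it?** No. Section 8.2 lists 1 + 2 = 3 mixed models, one on STAI-6 and two on HRV, and 0 of 3 use the stress item. The correlations may use it, since their term for stress matches the purpose given for that item in section 5.3.2. But a correlation between changes does not estimate the difference between mindfulness and sham.

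5. **Is another self-report stress scale administered?** None is listed in section 5.3. The reference list contains three papers on perceived-stress scales (a source paper, an adaptation for EMA research and short-form norms), but no such scale appears among the measurements. The documents do not say why.

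6. **Is the stress item ready to be modelled?** Not yet. Its seven labels run from *Very Bad* (1) through *Same as Before* (4) to *Very Good* (7). Against a statement about feeling stressed, a 7 could mean strong agreement or a good, unstressed state. The scoring direction is therefore undefined.

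**The case against.** The strongest reply is that section 8.2 is open about its operational definition. It names the instrument, so a reader can see what was measured, and momentary tension and calm are close to what many people mean by momentary stress. Section 1 does present stress as a cause of chronic anxiety, but that is a pathology and not state anxiety, so the passage is weak evidence that the protocol separates the two momentary constructs. This stands, and it limits the point to an unjustified proxy label. The analysis itself is not invalid.

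Four stronger readings are tempting and are not supported.

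- *That the confirmatory result cannot bear on stress at all.* It could, if the sponsor prespecified and justified STAI-6 as a proxy. The documents simply do not do so.
- *That the stress item goes unanalysed.* The unnamed stress measure in the correlations may be this item. What is established is that it has no planned group comparison.
- *That the mismatch costs a calculable amount of effect or sample size.* The documents give no correlation between STAI-6 and stress. Assumed values of r from 0.3 to 0.9 give a shared variance r² of 0.09 to 0.81, which settles nothing. Turning r into a diluted effect also requires that mindfulness reaches STAI-6 only through stress. If it acts on anxiety directly, the STAI-6 effect could equal or exceed the effect on stress. Section 8.1 states no power, effect size or SD for such a factor to act on.
- *That every statement about stress should rest on the EMA item alone.* Section 1 declares HRV a measure of the stress response, and section 8.2 models it twice. The EMA item is a single question, and the documents cite no validation for it.

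**Conclusion.** The point holds in limited form. As documented, the confirmatory analysis supports a conclusion about state anxiety. The plan's conclusion about stress rests on a proxy for which it offers no argument. The direct stress item is collected at all six STAI-6 time points and has no planned comparison between arms.

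The size is a matter of what may be claimed, not of a number: the one confirmatory conclusion is mislabelled, and none of the three models uses the stress item. This rests only on the plan's own definitions and its list of analyses; no assumed correlation enters. It should be put right before data collection. Because this is a pilot and the group comparison on STAI-6 is usable as it stands, it is a fault in the outcome definition and does not undermine the design.

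**What to change.** - In section 8.2, state the STAI-6 outcome and the conclusion drawn from its Bayes factor as state anxiety. Alternatively, keep the stress wording and add an explicit justification, with a source, for STAI-6 as a stress proxy.
- Prespecify the same Group-by-Day mixed model for the EMA stress item as a secondary or exploratory outcome.
- Before data collection, replace the response labels on that item with intensity or agreement anchors and state which end means more stress.
- Name the instrument that supplies stress levels in the exploratory correlations.
- Base self-report statements about stress on the EMA item, alongside HRV as the declared physiological stress measure.

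The cost is a few sentences in section 8.2, edited labels in Qualtrics and one more run of a model already planned. No participants, items or assessment times are added. The downside is one more outcome to report, and it is a single item with no cited validation, so its result should be described with that limitation.

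### The sole confirmatory STAI-6 model has no pre/post term and does not use the pre-randomisation score: read literally it dilutes the Group effect, and read as post scores only it loses precision

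*Combined protocol and SAP*

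**What the plan says.** Section 5.3.2 sets the measurement schedule: "The STAI-6 will be administered twice daily: once before and once after listening to each audio track". Over three days that makes six scores per person, three before and three after a track. Section 5.4 places the first of them ahead of allocation. On Day 1 "Pre-intervention assessments of STAI-6, EMA will also be conducted", and only after the HRV reading that follows does the survey software randomise. The Day 1 pre-score is therefore a true baseline. The other two pre-scores come after randomisation.

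Section 8.2 names one confirmatory analysis: "Bayesian mixed-effects models to investigate the longitudinal changes in self-reported stress measured via STAI-6". STAI-6 is the "dependent variable, with 'Group' (mindfulness intervention or control), 'Day' (1 to 3), and their interaction term as independent variables", with a random intercept for participant. The decision rule is: "A BF10 greater than 1 will indicate slightly positive evidence supporting the effectiveness of the mindfulness condition over the control condition in stress reduction". Section 8.2 does not say which of the six scores enter. It contains no term separating pre from post and no baseline covariate, and it does not say which coefficient, comparison model or prior defines BF10.

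Two exploratory HRV models follow. The first is worded like the STAI-6 model. The second spells out a change outcome: "HRV (calculated by the difference in pre- and post-meditation HRV scores".

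**The concern.** The model should estimate how far mindfulness lowers stress relative to sham. A Group term fitted to all six scores averages over occasions when the day's track had not yet been heard, one of which no treatment could have affected. That estimates a smaller quantity than the post-session benefit. Restricting the outcome to post scores removes the dilution, but it leaves out the one covariate most likely to explain differences between people. The plan expects a small effect ("we will anticipate a modest yet discernible reduction in stress levels compared to a control condition") in about 50 people, so neither loss is trivial.

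The model also contains both Group and Group×Day. An analyst who reads the stated interest in change over time as pointing to the interaction would be testing whether the benefit differs between days, not whether there is one.

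**Working it through.** **Inputs.** The plan gives no effect size, variance or power for this analysis, so there is no figure on this point to reproduce. Its only design figure is 60 recruits, which is 50 × 1.20. From section 8.1 ("ensuring we meet our target of at least 50 participants") I take 50 analysed and assume 1:1 allocation, giving 25 per arm. Further assumptions:
- one score has variance 1, split into person (P), day (S) and residual (R) parts;
- the post-session benefit d is the same each day;
- a fraction c of d is still present at the next day's pre-score and does not accumulate.

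**Step 1: what the Group term estimates.** The expected arm differences are 0, cd, cd for the three pre-scores and d, d, d for the three post-scores.
- All six scores: (0 + 2cd + 3d)/6 = d(3 + 2c)/6. This is d/2 at c = 0, 2d/3 at c = 0.5 and 5d/6 at c = 1. With d = 0.50 the values are 0.25, 0.33 and 0.42.
- Post scores only: 3d/3 = d, whatever c is.

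These fractions do not depend on the variance split.

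**Step 2: precision.** The variance of a person's mean is P + S/3 + R/6 for all six scores and P + S/3 + R/3 for post scores. The covariance of the Day 1 pre-score with the mean post score is P + S/3, so r = (P + S/3)/√(P + S/3 + R/3). Adjustment multiplies the post-score variance by 1 − r².

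| P, S, R | all six | post only | r | r² | post adjusted |
|---|---|---|---|---|---|
| 0.5, 0.2, 0.3 | 0.617 | 0.667 | 0.69 | 0.48 | 0.346 |
| 0.3, 0.35, 0.35 | 0.475 | 0.533 | 0.57 | 0.33 | 0.360 |
| 0.6, 0.1, 0.3 | 0.683 | 0.733 | 0.74 | 0.55 | 0.332 |
| 0.5, 0, 0.5 | 0.583 | 0.667 | 0.61 | 0.375 | 0.417 |

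The covariate thus removes 33-55% of the variance in these splits. If r were 0.3, it would remove 0.3² = 9%.

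**Step 3: illustrative power.** The standard error is √(2V/25), and power comes from the noncentral t with 48 df (47 when adjusted). For the first split with d = 0.50 and c = 0:
- all six: 0.25/√(2 × 0.617/25) = 0.25/0.222 = 1.13, power about 20%;
- post only: 0.50/0.231 = 2.16, about 56%;
- adjusted: variance 0.346 × (1 + 1/46), the factor allowing for chance imbalance in the covariate, gives 0.50/0.168 = 2.98, about 83%.

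Ranges over the four splits:

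| d | all six, c = 0 | all six, c = 1 | post only | post adjusted |
|---|---|---|---|---|
| 0.50 | 18-24% | 42-55% | 53-66% | 76-84% |
| 0.30 | 10-12% | 18-24% | 23-30% | 36-43% |
| 0.20 | 7-8% | 11-13% | 13-16% | 19-22% |

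A different covariance gives the same picture. With a common correlation of 0.6 among all six scores, the variances are (1 + 5 × 0.6)/6 = 0.667, (1 + 2 × 0.6)/3 = 0.733 and 0.733 − 0.36 = 0.373. Power at d = 0.50 is then 19%, 54% and 83% (normal approximation, c = 0).

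**Step 4: the interaction.** On post scores the arm difference is d on each day, so every Group×Day contrast is d − d = 0. With a constant 0.50 SD benefit the interaction test rejects in 5% of trials, as under no effect.

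**Step 5: the prior.** Take a two-group Cauchy prior as an approximation to the mixed model. BF10 = 1 then falls at |t| = 1.66, 1.77 or 1.89 for scales 0.5, 0.707 or 1.0. With no effect, that cut-off is passed in 10.3%, 8.3% or 6.5% of trials. On these cut-offs the covariate gains 12-30 points at d = 0.50.

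**The case against.** - **This is a pilot, and BF10 above 1 is called only slight evidence.** True, and it limits the harm. But the plan itself labels this analysis confirmatory and attaches a statement about effectiveness to it.
- **Omitting a baseline covariate is not an error.** It causes no bias in a randomised post-score comparison, and a reader who inferred bias would be wrong. The loss is one of precision, and its size depends on r. The random intercept does not make up for it: it represents correlation within a person but does not remove a chance baseline difference between arms.
- **The decision rule speaks of mindfulness over control, which points to Group.** That is the more natural reading. It still does not settle Group against Group×Day when both are in the model.
- **A change-score outcome may be meant.** A reader might infer this from the reference to longitudinal changes, and go on to conclude that the estimate could fall to one third of d. The documents do not support that. The first HRV model, on undifferenced HRV, uses the same phrase, and the plan writes out a change score where it wants one. The one-third figure also needs full carry-over that does not accumulate: d(3 − 2c)/3 at c = 1. If benefit accumulates from day to day, the change estimate is d at every c.
- **The power figures use a criterion the plan does not have.** Correct. They compare the readings with each other and are not operating characteristics of the BF10 rule.

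**Conclusion.** The concern holds. Taken literally, with six scores and no pre/post term, the confirmatory model treats a pre-randomisation score and two further pre-session scores as outcomes. Its Group effect is one half to five sixths of the post-session benefit, assuming equal daily benefit and carry-over that does not accumulate. Restricted to post scores, it is unbiased but gives up a share r² of the variance: 33-55% in the assumed splits, 9% if r is 0.3. At an assumed 0.50 SD with 25 per arm, the illustrative power is 18-24% for all six scores without carry-over, 53-66% for post only and 76-84% for adjusted post.

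A reader might take the missing prior and comparison model to be the main fault. They are needed to compute BF10 and should be stated, but they are accompanying detail. The substantive problem is which scores are modelled and the unused baseline.

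**What to change.** In section 8.2, make post-session STAI-6 on Days 1-3 the dependent variable. Include Group, Day, Group×Day, the Day 1 pre-session STAI-6 as covariate and a participant random intercept. Code Day with sum-to-zero contrasts so that the Group coefficient is the three-day average. Base BF10 on that coefficient, against the same model without it. State the family and scale of the prior, with a sensitivity range of scales. Report Group×Day as secondary and within-session change as supportive.

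The cost is SAP wording and one extra covariate, since every value is already collected. The Day 2 and Day 3 pre-scores become supportive data. If there is no carry-over, a change-score analysis would be more powerful: 85-97% against 76-84% at 0.50 SD. The 85-97% comes from a t-test on each person's mean change, which a random-intercept model of change scores need not reproduce exactly. If the sponsor prefers the within-session effect, the plan should name the change score as the outcome and say that benefit carried overnight is then not counted.
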